A secondary objective is to evaluate the need for delayed imaging for relative MPI assessment (per ASNC 2016 guidelines: 15-45-minute delay for Stress; 30-60 minutes for Rest ) ("delayed imaging"). The current MBF protocol requires additional imaging sessions to accommodate a dynamic acquisition during tracer injection for MBF calculation and delayed imaging post-injection for static MPI evaluation. PET protocols with Rb and N-ammonia use the latter portion of the dynamic imaging series for relative MPI assessment. Studies that have considered this for SPECT tracers have had mixed results . Images acquired as part of the feasibility study will provide pilot data for evaluating the potential to use the latter portion of the SPECT MBF dynamic acquisition for relative MPI assessment. Additional secondary objectives are to assess the impact of measuring SPECT MBF on patient throughput and to evaluate a 50% reduction in the activity used to measure SPECT MBF.

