## 1.2 Hypotheses

- a) Primary hypotheses
- 1. Feasibility: It is practical to obtain reliable SPECT measurements of MBF routinely within the workflow of a standard clinical practice.
- 2. MBF reproducibility: Global MBF measured at remote sites will agree within 10% with the same data processed at an expert core laboratory.
- b) Secondary hypotheses
- 1. Impact on throughput: Routine implementation of a SPECT MBF protocol will have at most minimal impact on patient throughput (defined as <10% reduction in patient volumes).
- Delayed imaging: static reconstruction of the last 6 min of the dynamic acquisition will provide images that are clinically equivalent (less than 10% change in patient diagnosis from normal (summed stress score < 4) to abnormal or vice versa), compared to standard static images obtained following a 45-min delay post-injection.
- 3. Half-dose MBF measurement: The difference between MBF measurements with full-data and half-data dynamic acquisitions will be less than or equal to the inter-observer variation in MBF measurements with full-data.

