## 3. Study Design

Patients will be recruited from those referred to the local site's Diagnostic Imaging Department for SPECT myocardial perfusion imaging (MPI) and who have an intermediate to high pre-test likelihood of disease (Diamond-Forrester criteria ≥ 30%). Research imaging will consist of a SPECT acquisition at the time of rest and stress radiotracer injection in addition to the standard (delayed) clinical stress/rest SPECT scan with 99mTc-tetrofosmin. This is an observational study; patients will be managed according to the standard clinical care of the local site. Where available, a CT scan will also be acquired for attenuation and/or scatter correction. Studies may be one day (rest/stress or stress/rest) or two day (rest and stress on separate days)

Study end will be defined as completion of all SPECT imaging at rest and stress.

A core lab will be established at the University of Ottawa Heart Institute. Initial studies acquired at the local site according to the protocol will be evaluated for technical image quality (e.g. patient positioning, CT-SPECT coregistration, noise levels, patient motion and motion correction, artifacts). The core lab will work with local sites, as needed, to implement the protocol and ensure adequate data quality. All studies will be analyzed locally but the raw data will also be anonymized and forwarded to the core facility for reprocessing. Central processing will allow comparison between sites and the repeat processing will provide an estimate of inter-operator variability in the measurements. The core lab will also compare the relative perfusion from immediate and delayed imaging for image quality and diagnostic accuracy (visual and quantitative).

Studies will be acquired at 6 initial sites with mixed prior experience at MBF imaging, to demonstrate feasibility of use in a clinical setting. Each site will acquire 5 studies during an initial start-up period to become comfortable with the SPECT MBF protocol for data acquisition and processing. Studies acquired during the start-up period will not be used in the final analysis but will be processed by the core lab and used to evaluate site training. Following the start-up period, each site will acquire 25 studies within 60 working days to show that the protocol can be implemented without major disruption to clinical throughput.

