# 4.4.1 Stress Imaging

Patient will be positioned according to standard clinical practice for myocardial perfusion imaging with the heart centered in the field of view. Image data will be acquired in listmode for 11 min starting just prior to tracer injection. There should be no movement of the patient or camera from the start of the vasodilator injection through to the end of image acquisition. Stress will be induced using a vasodilator, either dipyridamole, adenosine, Adenosine Tri-phosphate or regadenoson according to local site preference.

- Dipyridamole: Dipyridamole (0.14 mg/kg/min over 4 or 5 min depending on local laboratory practice) will be given intravenously. 99mTc-tetrofosmin is injected at 3-5 minutes following the end of the dipyridamole infusion. Stress imaging will start immediately prior to the 99mTc-tetrofosmin injection. Aminophylline will be administered intravenously as needed, no earlier than 3 minutes following injection of tracer.
- Adenosine/Adenosine Tri-phosphate: Protocol will follow ASNC guidelines.
- Regadenoson: Protocol will follow ASNC guidelines.

The usual post-stress images (delayed stress) will be acquired as per standard clinical practice.

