## 4.4.2 Resting Images

If a stress-first protocol is being used, then the acquisition of additional resting imaging will be decided based on local-site standard clinical practice.

For rest imaging, the patient will be positioned according to standard clinical practice for myocardial perfusion imaging with the heart centered in the field of view. Image data will be acquired in listmode for 11 min starting just prior to tracer injection. There should be no movement of the patient or camera from the start of the tracer injection through to the end of image acquisition.

Acquisition of a clinical resting relative perfusion image (delayed rest) will be acquired as per standard clinical practice.

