## 4.5 Image Processing and Analysis

Following acquisition, the listmode data will be rebinned into 9x10s, 6x15s, 4x120s frames. The projection data for each frame will be independently reconstructed using manufacturer supplied MLEM iterative reconstruction that includes point-spread function modeling and a noise-suppression prior. A total of 60 iterations will be used corresponding to the manufacturer recommendation for resting (low-count) studies. Images will be filtered post-reconstruction using a 3D 5th-order Butterworth filter with a cut-off frequency of 0.37 cycles/cm. Images will be reconstructed without corrections (NC), and with attenuation correction (AC) when a CT attenuation scan is available. When applied, AC will be based on a CT scan acquired separately with the patient on the same configuration as used for the SPECT dynamic acquisitions.

The reconstructed dynamic image series will be processed using the kinetic analysis software tools provided by the manufacturer (GE Healthcare). With this semi-automatic software, a 1-tissue-compartment model will be fit to the myocardium time-activity data to generate a parameterized map of the uptake rate constant K1 (ml/min/g) for the heart. K1 values will be scaled to MBF based on the K1-MBF relationship determined from previous single-site comparisons of clinical SPECT and Rb82 PET studies .

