## 5. Sample Size and Analysis

Adverse events will be listed on an individual basis. All safety variables and demographic data will be tabulated with descriptive statistics, if appropriate.

Bland-Altman plots will be used to determine significant bias and the coefficient of repeatability of global and regional MBF and MFR measurements for the core versus local reproducibility studies and for measurements of MBF with full and half data reconstructions. The mean difference in MBF between core and local-site processing will be assessed with a paired t-test. A sample size of 25 studies per center provides 88% power (alpha=0.05) to detect a 10% difference, assuming a standard deviation in repeated MBF measurement of 15% (effect size of 0.67). Each center will recruit 5 practice patients and 25- 35 patients for analysis. There will be 6 centers and each center will recruit 30 - 40 patients for a minimum of 180 patients to a maximum of 240 patients(30 practice patients and 150 - 210 patients for analysis). Global and regional MBF at rest and stress will be separately compared. Differences in MFR will be similarly assessed.

To evaluate impact on patient throughput, the following information will be collected for each site and each MBF study:

Time patient enters the room

Time of radiotracer injection (for dynamic imaging sessions)

Start times of each image series (static and dynamic)

Time patient exits the room

Number of MPI studies done per day.

Each site will also provide number of MPI studies done per day for the 2-month period prior to starting to apply the MBF protocol and similar timing and demographic data for 25 standard (non-MBF) MPI studies.

MBF/MFR analysis will be repeated with attenuation corrected images for those data sets which include a transmission imaging.

Image quality will be assessed at the core lab. The following factors will be considered:

- Tracer bolus quality: start of bolus is imaged, bolus duration is appropriate (total activity in the FOV is within 10% of final frame value 3 minutes after start), single peak
- Positioning: Heart is within the quality FOV no truncation.

<sup>1 G\*Power software, version 3.1.3. Faul F, Erdfelder E, Lang A-G, and Buchner A. G\*Power 3: A flexible statistical power analysis program for the social, behavioral, and biomedical sciences. *Behavior Research Methods*, 39:175–191, 2007

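### The delayed-imaging hypothesis names a 45-min comparator that the available acquisition text does not require, and the comparison is not tied to the delay actually used

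*Combined protocol and SAP*

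**What the plan says.** The delayed-imaging hypothesis is a secondary hypothesis in Section 1.2. A static image rebuilt from the end of the dynamic scan is to be clinically equivalent "compared to standard static images obtained following a 45-min delay post-injection". Equivalence means that under 10% of patients cross the normal/abnormal boundary, which is a summed stress score of 4. The stress image therefore decides the result.

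The rest of the protocol treats the delay as follows:

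- **Section 1.1** describes delayed imaging by a cited guideline: "15-45-minute delay for Stress; 30-60 minutes for Rest".
- **Section 4.4.1** (stress): "The usual post-stress images (delayed stress) will be acquired as per standard clinical practice".
- **Section 4.4.2** (rest): "Acquisition of a clinical resting relative perfusion image (delayed rest) will be acquired as per standard clinical practice".
- **Section 3** adds that "patients will be managed according to the standard clinical care of the local site".
- **Appendix A** illustrates the imaging timelines. The figures are not shown in the text available for review. The captions to Figures 1a, 2a and 3 give scan lengths, infusion time and the wait before tracer injection, and say that these times can be changed in line with the protocol text. No caption gives an interval from injection to the delayed scan.
- **Section 5** has two blinded core-lab readers score the immediate and delayed images. It sets no eligibility window, stratification or adjustment by delay. The injection time and the time at which each series begins are collected, but for the throughput question.

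**The concern.** The hypothesis is about one contrast, immediate against 45 min. The available acquisition text allows a family of contrasts, and for stress 45 min is the upper end of the cited range. Nothing in Section 5 ensures that the images compared are those the hypothesis names.

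The question is whether waiting changes the diagnosis. If it does, a shorter wait would plausibly show less change. Sites that image early in the range could then hold the observed proportion under 10%, and the trial could report that a 45-min delayed image is unnecessary when many of its comparators were taken well before 45 min. Section 1.1 says that earlier SPECT work on this question gave mixed results, so the answer cannot be taken as settled.

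**Working it through.** **Plan's own timing.** Section 4.4.1 states: "Image data will be acquired in listmode for 11 min starting just prior to tracer injection". Section 4.5 states that "the listmode data will be rebinned into 9x10s, 6x15s, 4x120s frames". The frames sum to 9×10 + 6×15 + 4×120 = 90 + 90 + 480 = 660 s = 11 min, so the two sections agree. The last 6 min run from 11 − 6 = 5 min to 11 min, with midpoint 8 min. These are approximate times after injection, because the scan starts just before it.

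**Separation from the delayed stress scan.** The range of 15 to 45 min is from Section 1.1. The 3-min delayed stress scan is the example in the Appendix A captions.

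| Delayed scan starts (min) | Gap from end of dynamic scan (start − 11) | Midpoint gap (start + 1.5 − 8) |
|---|---|---|
| 15 | 4 min | 8.5 min |
| 30 | 19 min | 23.5 min |
| 45 | 34 min | 38.5 min |

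Between the ends of the range, the contrast in time differs by 38.5/8.5 ≈ 4.5-fold on midpoints, or 34/4 = 8.5-fold on end-to-start gaps. These are ratios of time, not of diagnostic change.

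**What this could do to the criterion (illustration on assumed rates).** The documents give no change rate at any delay and no site's delay. Suppose *k* of 6 sites use short delays, with 25 patients per site (150 in all, the Section 5 minimum for analysis). Let the true change rate be p45 against a 45-min image and pS against a short-delay image. Then:

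- pooled rate = [k·pS + (6 − k)·p45]/6;
- success = observed change under 10%, that is, at most 14 of 150.

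For p45 = 15% and k = 3, the pooled rate is (3×2% + 3×15%)/6 = 8.5% if pS = 2%, and (3×5% + 3×15%)/6 = 10.0% if pS = 5%. Binomial simulation gives these chances of success:

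| Assumed p45 | k = 0 | k = 3 (pS 5% to 2%) | k = 4 (pS 5% to 2%) |
|---|---|---|---|
| 12% | 19% | 71% to 90% | 86% to 99% |
| 15% | 3% | 46% to 71% | 73% to 95% |
| 20% | about 0% | 14% to 30% | 46% to 79% |

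The chance of success first passes one half with two short-delay sites if p45 is 12%, three or four if it is 15%, and four or five if it is 20%. If the change rate does not depend on delay (pS = p45), mixing delays has no effect at all.

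**Number of discordant cases.** If the criterion is met, at most 14 of 150 or 20 of 210 patients change class. With 6 sites, and delay set largely by site, there is little information with which to model change against delay.

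The only power figure in Section 5 (88%) concerns core-versus-local MBF and does not bear on this hypothesis.

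**The case against.** The strongest reply is that 45 min lies inside both cited ranges, so sites may in fact image at or near it. The lost Appendix A figures may also show the interval. Section 1.1 calls these pilot data and Section 2 speaks of exploring optimization. A comparison with whatever each site normally does is a legitimate pragmatic question, and the recorded times allow the delay to be recovered later.

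Much of this stands. It limits the point to a secondary hypothesis and to a possibility. It does not remove the mismatch: the captions make the illustrated times adjustable in line with the protocol text, and the available text sets no delay. The pragmatic question is sound, but it is not the one written in Section 1.2. Recorded times help only if the plan says how they will be used.

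Three stronger readings are tempting, and the documents do not support them:

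- **That the plan pools all delayed images whatever their delay.** Section 5 is silent on this; it specifies neither pooling nor stratifying.
- **That the result will be biased toward equivalence.** No site's delay is reported, and 15 min is the lower bound of a guideline range, not a known practice. Nothing in the documents links diagnostic change to delay. Discordance also reflects reader variation and scan length (6 min immediate against 3 min delayed in the stress example).
- **That a 4.5-fold difference in gap measures the bias.** It describes timing only and changes to 8.5-fold under another definition of the gap.

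**Conclusion.** The concern holds as an unreconciled comparator. Section 1.2 fixes 45 min. Section 1.1 allows 15 to 45 min for stress, the available text of Sections 4.4.1 and 4.4.2 sets no delay, and Section 5 does not tie the comparison to the delay used. If some sites image early in the range, a change rate below 10% would not be a test against a 45-min image.

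What can be sized is the separation: 4 min at one end of the stress range and 34 min at the other, measured from the end of the dynamic scan. A lean toward equivalence is plausible, but its size cannot be determined from the documents. In the illustration it runs from nothing, if change does not depend on delay, to a reversal of the likely conclusion, if several sites use short delays and change depends strongly on delay. The conclusion rests on the surviving text, since the Appendix A figures could not be read. The primary hypotheses are not affected.

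**What to change.** 1. Reconcile Section 1.2 with Sections 1.1, 4.4.1 and 4.4.2 by restating the comparator as the site-standard delayed image at its recorded delay. This prescribes no delay and changes no patient's imaging.
2. State in Section 5 that the injection-to-delayed-image interval will be derived for every stress scan from the times already collected, and report its distribution by site.
3. Report the proportion changing class, with a confidence interval, overall and descriptively by actual delay. Fix in advance, before the images are read, a window centred on 45 min, so that scans just short of 45 min are not split from those just over it.
4. Limit any statement of equivalence to a 45-min image to scans inside that window.
5. Omit a regression of discordance on delay, or label it exploratory. Delay is confounded with site, and so possibly with stress agent and protocol order, and discordant cases will be few.

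The cost is plan wording and one table, with no new data. The 45-min statement will rest on fewer scans. For example, if one third of scans fell inside the window (an assumption), its interval would be about √3 ≈ 1.7 times as wide at the same change rate. If few or no scans fall inside it, the trial could not make a 45-min statement, and the report should say so.

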## 4.3 Radiotracer

The tracer to be used is 99mTc-tetrofosmin. 99mTc-tetrofosmin will be mechanically delivered using a syringe pump at a constant rate over a 30 s period, followed immediately by a saline flush at the same injection rate as the tracer. The volume of the saline flush should be greater than the volume of the lines connecting the pump to the patient to ensure that the full tracer activity is delivered. There should be no delay between tracer and saline flush injections. Manual injection of radiotracer will not be used for this study to increase standardization but will be evaluated in future studies.

The measurement of CFR with CZT SPECT has been validated with full doses of radiotracer but is most likely possible with half doses. For this feasibility study, full doses will be used to provide the best CFR results possible. The listmode data from the full-dose studies with be reprocessed by the core laboratory to simulate half doses and

confirm that half doses are adequate. The planned subsequent studies of diagnostic accuracy and prognosis would evaluate half doses.

The activity of the radiotracer injected at stress and rest will be full clinical doses with a minimal activity of 370 MBq for the first study and 1100 MBq for the second study for a one day protocol. Injected doses will be 370 MBq at both rest and stress for 2-day protocols.

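### The half-dose criterion has no fixed limit and undefined measures, so its margin widens as observers agree less, and no rule limits a systematic full-versus-half bias.

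*Combined protocol and SAP*

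**What the plan says.** Section 1.2, secondary hypothesis 3, states that the difference between full-data and half-data MBF "will be less than or equal to the inter-observer variation in MBF measurements with full-data". It gives no number. It does not say whether the difference is a mean, an absolute difference or a limit of agreement, or whether the variation is an SD, a coefficient of repeatability or something else.

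The other quantitative hypotheses in Section 1.2 (core-site agreement, throughput, delayed imaging) each carry a fixed 10%. Primary hypothesis 2, for example, reads "Global MBF measured at remote sites will agree within 10% with the same data processed at an expert core laboratory".

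Section 5 plans Bland-Altman bias and coefficient of repeatability both for core versus local processing and "for measurements of MBF with full and half data reconstructions", without an acceptance limit for either output in the half-data comparison. It also has two experienced core-laboratory readers supply inter-observer repeatability, so the yardstick comes from the trial itself. The only planning value for measurement variability is in the sample-size statement, "assuming a standard deviation in repeated MBF measurement of 15" per cent.

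Section 4.3 gives the purpose of the half-data reprocessing: to "confirm that half doses are adequate".

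**The concern.** A margin set by observer disagreement in the same trial moves the wrong way: the noisier the readings, the larger the half-data discrepancy that is accepted. It also risks mixing two kinds of error. Observer scatter varies in direction from patient to patient, whereas a bias shifts the average. If scatter becomes the allowance for a mean shift, a consistent half-data error can be accepted because readers happen to disagree.

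Section 5 would show such a shift, but nothing makes it count against hypothesis 3. The trial could report a clear mean difference and still declare half data adequate. That conclusion would then inform the later accuracy and prognosis studies mentioned in Section 4.3.

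**Working it through.** **Inputs from the plan (Section 5).** SD 15%; detectable difference 10%; 25 studies per center; 150 to 210 studies for analysis (150 used here).

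**Assumptions.** The 15% SD applies between observers, with mean observer difference 0. The full-half SD, *w*, is not in the documents; 5%, 10% and 15% are tried. Differences are normal.

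**1. The plan's own figure.** Section 5 says: "A sample size of 25 studies per center provides 88% power (alpha=0.05) to detect a 10% difference". The exact two-sided paired t-test (24 df) with effect size 10/15 = 0.67 gives 89.2%, close enough to 88%. If 15% were the SD of a single reading, the SD of differences would be 15 × √2 = 21.2% and power 61.9%. So 15% is being used as an SD of paired differences, in line with the stated "effect size of 0.67".

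**2. Size of the margin at SD 15%.**
- SD: 15.0%
- Coefficient of repeatability: 1.96 × 15 = 29.4%
- Mean absolute difference: 15 × √(2/π) = 12.0%
- Within-observer SD: 15/√2 = 10.6%
- Median absolute difference: 0.674 × 15 = 10.1%

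All exceed 10%.

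**3. Mean difference compared with a spread.** The mean has variance *w*²/150. The estimated observer SD has variance of about 15²/(2 × 149). For a true 12% bias against the SD, the pass probability is about Φ(3 / √(*w*²/150 + 225/298)):
- *w* = 5: Φ(3/0.960) = 99.9%
- *w* = 10: Φ(3/1.192) = 99.4%
- *w* = 15: Φ(3/1.502) = 97.7%

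Simulation agrees. Pass rates with 150 studies and observer SD 15%:

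| True bias | Mean vs SD | Mean vs 1.96 SD |
|---|---|---|
| 10% | 100% | 100% |
| 12% | 98-100% | 100% |
| 15% | 49% | 100% |
| 20% | 0% | 100% |

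**4. Like compared with like.** Pass rates for a true 11% bias, 150 studies, observer SD 15%:

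| Measure compared | *w* = 5% | *w* = 10% | *w* = 15% |
|---|---|---|---|
| Mean vs mean | 0% | 0% | 0% |
| Mean absolute difference | 87% | 34% | 0.4% |
| Root mean square | 99.9% | 54% | under 1% |
| Outer limit of agreement | 100% | about 45% | 0% |
| SD vs SD (same as coefficient of repeatability) | 100% | 100% | 50% |

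The last row does not respond to bias at all, because an SD of differences ignores their mean.

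**5. If observers agree better than 15%.** For a true 10% bias:
- Mean vs SD: passes 49% at observer SD 10%, 0.1-6% at 8%, and 1% or less at 7%.
- Mean vs 1.96 SD: passes 100% at observer SD 10%, and still 38-44% at 5%.

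**6. A fixed limit on the bias.** With the 90% CI required to lie within ±10%, the pass probability is about Φ((10 − *b*)√n/*w* − 1.645):
- *b* = 10: Φ(−1.645) = 5%
- *b* = 5, *w* = 15, n = 150: Φ(4.082 − 1.645) = 99.3% per condition; rest and stress both, if independent, 0.993² ≈ 98.5%
- *b* = 5, *w* = 15, n = 100 (assumed number of rest studies): Φ(3.333 − 1.645) ≈ 95%

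**The case against.** A reader might infer that the plan will pass a half-data bias larger than 10%. The documents do not support that as a flat statement. The high pass rates in step 3 need a mean to be compared with a spread, and no section prescribes that pairing. Section 5 applies the same Bland-Altman outputs to both comparisons, so comparing like with like is at least as natural, and a mean-versus-mean rule would block the bias. This stands: what the text supports is an undefined and uncapped criterion, with consequences that depend on how it is read.

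The 15% is stated for the core-versus-local comparison: "The mean difference in MBF between core and local-site processing will be assessed with a paired t-test". Two experienced readers in one laboratory may well agree better. Section 3 does describe repeat processing at core and site as a source of inter-operator variability, so 15% is a plausible input, but it remains an assumption.

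The 10% limit is written for remote-versus-core global MBF, and nothing requires half-data agreement within it. Benchmarking against observer variability is a legitimate choice for spread.

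No document shows that half data shift MBF in one direction. Section 4.5 describes the 60 iterations as the manufacturer's recommendation for low-count studies. The point is only that the rule may fail to exclude a shift.

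Nor should a reader infer that half dose would be adopted on this result. Section 2 calls the work exploratory, patients here receive full doses, and Section 4.3 says later studies would evaluate half doses. With 150 studies, the Bland-Altman analysis would almost certainly detect a 10% bias. It would be visible, but it would not be part of the pass rule.

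**Conclusion.** The concern holds in a limited form. Hypothesis 3 has a floating margin and undefined measures, and no rule limits the full-half bias. How large a bias could pass depends on two things the plan leaves open: the measures compared and the full-half SD. At an assumed observer SD of 15%, a 12% bias passes about 98-100% of the time when a mean is set against the SD or 1.96 SD. An 11% bias passes from 0% to 100% when like measures are compared. Against the SD, the problem largely goes away once observer SD is about 7-8% or less. Against the coefficient of repeatability it persists at 5%. Severity is modest: this is a secondary hypothesis in a feasibility study, and the remedy is a cheap improvement.

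**What to change.** In Sections 1.2 and 5, keep the observer comparison for spread and state which like measures are compared, for example the full-half coefficient of repeatability against the inter-observer coefficient of repeatability. Since that comparison ignores bias, add a sentence such as: half data are called adequate only if the 90% CI of the mean full-minus-half percentage difference in global MBF also lies within ±10%, at rest and at stress separately. The figure from primary hypothesis 2 is the natural default; the sponsor may justify another, provided it is fixed in advance. If the condition fails, the conclusion is that a half-data bias has not been excluded, whatever the observer variation.

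The cost is one sentence and one CI from an analysis already planned, with no new patients or data. The half-dose claim becomes slightly harder to make, as step 6 shows. The rest comparison may have fewer studies, because Section 4.4.2 leaves rest imaging after a stress-first scan to local practice.
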